- A urine sample will be collected and sent to the central laboratory to assess compliance with the following background antidepressant medications: citalopram, escitalopram, fluvoxamine, fluoxetine, paroxetine, sertraline, and venlafaxine. All other SSRI/SNRI background antidepressants qualifying the subject for enrollment will be assayed (urine or blood sample) locally at the study site, if possible.
- Minimum criteria for the availability of documentation supporting the eligibility criteria are described in Section 17.4, Source Documentation.
- Subjects will administer the assigned study drug once daily at bedtime, approximately 3 hours after the last meal, from Day 1 to Day 167. Subjects are required to record the administration of study drug or any missed doses in subject diaries, which will be checked at each scheduled visit.
- Serum or urine pregnancy tests may be performed, as determined necessary by the investigator, to establish the absence of pregnancy at any time during the subject's participation in the study. A FSH test may also be performed at investigator judgment to assist in determining if a woman is of non-childbearing potential.
- Blood sample should be collected in fasting condition (at least 8 hours fasting). The serum chemistry also includes fasting glucose and insulin.
- FT4 analysis will be performed for subjects with known hypothyroidism who have been on stable treatment for at least 3 months prior to screening and otherwise for any subject with an elevated TSH.
- Where multiple procedures are scheduled for the same visit, procedures are recommended to be performed in the following order: ECGs, vital signs, blood draws, PRO assessments and then other procedures.
- Salivary cortisol samples (morning and evening) will be collected by subjects at home. Evening salivary cortisol samples (ie, on Days -1, 13, 41, 83, and 167) will be collected pre-dose, at bedtime. The morning sample will be collected upon awakening (ie, on Days 1, 14, 42, 84, and 168). Subjects should not consume alcoholic beverages for at least 12 hours prior to saliva sampling. Food, drinks (except water), and oral care (brushing, flossing, mouthwash) are not permitted 1 hour prior to the saliva collection.

- m. Biomarker samples should be collected under fasting conditions. Subjects should not participate in strenuous exercise or consume alcohol for 24 hours prior to collection.

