## **Clinical Laboratory Tests**

Blood samples for serum chemistry and hematology and a random urine sample for urinalysis will be collected. The investigator must review the laboratory results, document this review, and record any clinically relevant changes occurring during the study in the Adverse Event section of the CRF. The laboratory reports must be filed with the source documents. Clinical laboratory assessments (including TSH, FT4, hematology, serum chemistry, HbA1c, lipid panel, and urinalysis) should be performed under fasting conditions.

The following tests will be performed by the central laboratory:

- 
- Hematology Panel
    - hemoglobin
    - hematocrit
    - red blood cell (RBC) count
    - white blood cell (WBC) count with differential
    - platelet count
  
  - Serum Chemistry Panel
    - sodium
    - potassium
    - chloride
    - bicarbonate
    - blood urea nitrogen (BUN)
    - creatinine
    - glucose
    - insulin
    - aspartate aminotransferase (AST)
    - alanine aminotransferase (ALT)
    - gamma-glutamyltransferase (GGT)
    - total and direct bilirubin
    - alkaline phosphatase
    - creatine phosphokinase (CPK)
    - lactic acid dehydrogenase (LDH)
    - uric acid
    - calcium
    - phosphate
    - albumin
    - total protein
  
  - Lipid Panel
    - total cholesterol
    - triglycerides
    - low-density lipoprotein cholesterol
    - high-density lipoprotein cholesterol
  
  - Urinalysis
    - Dipstick
    - specific gravity
    - pH
    - glucose
    - protein
    - blood
    - ketones
    - bilirubin
    - urobilinogen
    - nitrite
    - leukocyte esterase
    - Sediment if dipstick result is abnormal
    - red blood cells
    - white blood cells
    - epithelial cells
    - crystals
    - casts
    - bacteria
  
  - Serum pregnancy testing, as determined by the investigator
  
  - TSH and FT4 (for subjects with known hypothyroidism who have been on stable treatment for at least 3 months prior to screening or for any subjects with an elevated TSH)
  
  - HbA1c
-

In addition, the following tests will be performed at the study site:

- Urine pregnancy testing, as needed per investigator's judgment
- Urine drug test (screening only): opiates (including methadone), cocaine, amphetamines, methamphetamines, cannabinoids, barbiturates, XTC and benzodiazepines. Urine drug screens will be done by the site using a dipstick
- Alcohol breath test

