### **Clinical Laboratory Tests**

Laboratory data will be summarized by type of laboratory test and treatment. Reference ranges and markedly abnormal results (specified in the SAP) will be used in the summary of laboratory data. Descriptive statistics will be calculated for each laboratory analyte at baseline and for observed values and changes from baseline at each scheduled time point. A listing of subjects with any laboratory results outside the reference ranges will be provided. A listing of subjects with any markedly abnormal laboratory results will also be provided.

The homeostatic model assessment will be conducted to estimate changes in beta-cell function and insulin sensitivity based on insulin and glucose laboratory values.

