1. INTRODUCTION

This statistical analysis plan (SAP) contains definitions of analysis sets, derived variables, and statistical methods for all planned analyses for the clinical study report (CSR) for study 42847922MDD2002.

This SAP does not include planned analyses on biomarkers or pharmacogenomics data or on pharmacokinetic (PK) and exposure/response analyses, which will be specified as appropriate in separate documents.

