6.2. Clinical Laboratory Tests

Descriptive statistics will be presented for thyroid-stimulating hormone (TSH) and free thyroxine (FT₄), as well as all chemistry (including the lipid panel), hematology (including hemoglobin A1c [HbA1c]), and urinalysis (pH and specific gravity) laboratory parameters at each scheduled time point. In addition, change from baseline to all postbaseline time points will be summarized for chemistry, hematology, urinalysis (pH and specific gravity), TSH, and FT₄ parameters and displayed by treatment group.

The number and percentage of subjects with treatment-emergent postbaseline markedly abnormal postbaseline values will be presented by treatment group. Clinical laboratory test values will be considered “treatment-emergent markedly abnormal” (TEMA) using the criteria defined by the sponsor listed in Attachment 4. The identification of TEMA laboratory values is based on the postbaseline value being out of range while the baseline value is either missing or within the range given in Attachment 4. If postbaseline laboratory results are above the upper limit and the baseline value is below the lower limit, then the postbaseline abnormality will also be considered TEMA. The same applies to the postbaseline value being below the lower limit with the baseline value being above the upper limit.

In addition, the number of subjects with the following shifts in chemistry laboratory values from baseline to the maximum postbaseline time point will be presented:

- Glucose:
 - from <100 mg/dL to ≥ 126 mg/dL (normal to high)
 - from <100 mg/dL to [≥ 100 mg/dL - <126 mg/dL] (normal to borderline high)
 - from [≥ 100 mg/dL - <126 mg/dL] to ≥ 126 mg/dL (borderline high to high)
- Triglycerides:
 - from <150 mg/dL to ≥ 200 mg/dL (normal to high/very high)
 - from <150 mg/dL to ≥ 500 mg/dL (normal to very high)
 - from [≥ 150 mg/dL - <200 mg/dL] to ≥ 200 mg/dL (borderline high to high/very high)
 - from [≥ 150 mg/dL - <200 mg/dL] to ≥ 500 mg/dL (borderline high to very high)
 - from [≥ 200 mg/dL - <500 mg/dL] to ≥ 500 mg/dL (high to very high)
- Total Cholesterol
 - from <200 mg/dL to ≥ 200 mg/dL (normal to borderline high/high)
 - from <200 mg/dL to ≥ 240 mg/dL (normal to high)
 - from <200 mg/dL to [≥ 200 mg/dL - <240 mg/dL] (normal to borderline high)
 - from [≥ 200 mg/dL - <240 mg/dL] to ≥ 240 mg/dL (borderline high to high)
- HDL Cholesterol: from ≥ 40 mg/dL to <40 mg/dL (normal to low).

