The following conversion rules will be used: Glucose 1 mg/dL=0.05551 mmol/L; Triglycerides 1 mg/dL=0.01129 mmol/L; Total Cholesterol, HDL Cholesterol 1 mg/dL=0.02586 mmol/L.

The incidence of subjects with treatment-emergent ALT values >3 *upper normal limit (ULN), AST > 3 *ULN, or total bilirubin >2 *ULN will be presented for the double-blind phase. Additionally, incidence of treatment-emergent hepatic toxicity (suspected Hy's Law⁴ cases) defined as (ALT values >3 *ULN or AST values > 3 *ULN) AND total bilirubin values >2 *ULN will be presented for the double-blind phase. Similar to the markedly abnormal analysis, only subjects with baseline (ALT values ≤ 3 *ULN or AST ≤ 3 *ULN) (AND baseline total bilirubin values ≤ 2 *ULN for hepatic toxicity) (or if baseline value is missing) will be eligible for these analyses.

A listing of subjects with markedly abnormal laboratory values will be provided.

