ATTACHMENT 4 CRITERIA FOR TREATMENT-EMERGENT MARKEDLY ABNORMAL LABORATORY VALUES

Laboratory Parameter (unit)	Markedly Abnormal Limits	
	Low	High
Clinical Chemistry		
Albumin (g/dL) but SI unit = g/L	2.4→24	6.0 →60
Alkaline phosphatase (U/L)	N/A	250
Alanine transaminase (SGPT) (U/L)	N/A	200
Aspartate transaminase (SGOT) (U/L)	N/A	250
Bicarbonate (mEq/L) but SI unit=mmol/L	15.1→15.1	34.9→34.9
Bilirubin (direct) (mg/dL) but SI unit = μ mol/L	N/A	3.0 mg/dL→51.3 μ mol/L
Bilirubin (total) (mg/dL) but SI unit = μ mol/L	N/A	3.0 mg/dL→51.3 μ mol/L
Blood urea nitrogen (mg/dL) but SI unit=mmol/L	N/A	50 mg/dL→17.9 mmol/L
Calcium (mg/dL) but SI unit=mmol/L	6→1.497 mmol/L	12→2.994 mmol/L
Chloride (mEq/L or mmol/L)	94	112
Cholesterol (mg/dL) but SI unit=mmol/L	N/A	300→7.758 mmol/L
Creatine kinase (U/L)	N/A	990
Creatinine (mg/dL) SI unit= μ mol/L	N/A	3→ 265.2 μ mol/L
Gamma glutamyl transferase (U/L)	N/A	300 U/L
Glucose Plasma (mg/dL) but SI unit=mmol/L	40→ 2.204 mmol/L	300→16.653 mmol/L
High-density lipoprotein cholesterol (HDL) (mg/dL) but SI unit=mmol/L	35→0.905	N/A
Lactic acid dehydrogenase (LDH) (U/L)	N/A	500
Low-density lipoprotein cholesterol (LDL) (mg/dL) but SI unit=mmol/L	89→ 2.3015	160→4.1376 mmol/L
Phosphate (mg/dL) but SI unit=mmol/L	2.2→0.71038 mmol/L	8.1→ 2.61549 mmol/L
Potassium (mmol/L)	3.0	5.8
Sodium (mEq/L) but SI unit = mmol/L	125→125	155→155
Total protein (g/L)	50	N/A
Triglycerides (mg/dL) but SI unit=mmol/L	N/A	500→5.645 mmol/L
Uric acid (mg/dL) but SI unit= μ mol/L	1.5→89.22	10→594.8 μ mol/L
Hematology		
Hematocrit (%) - female	0.28	0.50
- male	0.24	0.55
Hemoglobin (g/dL) but SI unit=g/L	8→80	19→190
Hemoglobin A1c (%)	4	8
Neutrophils (%)	30	90
Monocytes (%)	N/A	20
Eosinophils (%)	N/A	10
Basophils (%)	N/A	6
Lymphocytes (%)	10	60
Reticulocytes (%)	0.5	1.5
Platelet count (10^9 /L; giga/L)	100	600
Red blood cell (RBC) count (10^{12} /L; tera/L) - female	3.0	5.5
- male	3.0	6.4
White blood cell (WBC) count (10^9 /L; giga/L)	2.5	15.0
Urinalysis		
Urine pH	N/A	6.5
Urine specific gravity	< 1.001	> 1.035

Note: Values should be flagged as markedly abnormally low if the value is less than the value indicated in the “Low” column. Likewise, values should be flagged as markedly abnormally high if the value is greater than the value indicated in the “High” column.

Note: The same limits apply to both males and females unless gender is indicated.

N/A = Not applicable.

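### The SAP drops the protocol's reference-range summary and out-of-range laboratory listing; TSH, which has no other laboratory flag, shows the effect (minor)

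*SAP*

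**What the plan says.** Protocol 11.8, under Clinical Laboratory Tests, makes two relevant commitments. For the summary: "Reference ranges and markedly abnormal results (specified in the SAP) will be used in the summary of laboratory data". For individual subjects: "A listing of subjects with any laboratory results outside the reference ranges will be provided". It then promises a second, separate listing for markedly abnormal results.

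SAP Section 1 says that the SAP holds the "statistical methods for all planned analyses for the clinical study report (CSR"). It sends biomarker, pharmacogenomic, pharmacokinetic and exposure/response analyses to other documents. Safety laboratory data are not among these exceptions.

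For thyroid tests, SAP 6.2 begins: "Descriptive statistics will be presented for thyroid-stimulating hormone (TSH") and FT4. It adds change from baseline by treatment group. The count of treatment-emergent markedly abnormal values uses the Attachment 4 limits, where "values should be flagged as markedly abnormally high if the value is greater than the value indicated in the" High column, with a matching rule for low values. The one laboratory listing is: "A listing of subjects with markedly abnormal laboratory values will be provided".

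The Time and Events Schedule places TSH at screening, Week 12 and Week 24. FT4 is run for subjects with known, stably treated hypothyroidism "and otherwise for any subject with an elevated TSH". Separately, protocol 9.7 tells investigators to review laboratory results and "record any clinically relevant changes occurring during the study in the Adverse Event section of the CRF".

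**The concern.** A listing of everything outside the reference range and a listing of markedly abnormal values are different outputs. The second is narrower, and it cannot contain an analyte that has no markedly abnormal limit. If the report is programmed from the SAP, the first listing disappears, and an analyte without limits is left with group summaries only.

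Laboratory parameters are part of the stated safety objective. For TSH the useful safety information is how many subjects newly left the reference range in each arm, in which direction, and who they were. Arm means and mean changes do not show that. The trial could collect TSH three times in completers and still produce no laboratory output that counts or identifies a new abnormality.

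**Working it through.** No arithmetic is needed beyond counting. The check sets the protocol's commitments beside each laboratory output in SAP 6.2.

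**Step 1. Protocol commitments against the SAP**

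| Protocol 11.8 commitment | SAP 6.2 |
|---|---|
| Descriptive statistics and change from baseline | Present |
| Reference ranges used in the summary | No general summary; multiples of the upper limit of normal (ULN) for ALT, AST and total bilirubin only |
| Listing of any result outside the reference ranges | Absent |
| Listing of markedly abnormal results | Present |

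So 1 of the 2 promised laboratory listings is carried over. The SAP amendment history does not record removal of the other. The only change it records for Section 6.2 is the addition of unit conversion rules. SAP 6.2 and Attachment 4 show no redaction that could hide the missing output.

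**Step 2. Outputs that could flag a TSH or FT4 value**

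- Attachment 4 limits: 24 chemistry + 12 hematology + 2 urinalysis = 38 parameters (hematocrit and red cell count taken once each). TSH or FT4: 0.
- Shift definitions: glucose 3 + triglycerides 5 + total cholesterol 4 + HDL cholesterol 1 = 13. TSH or FT4: 0.
- ULN-based counts: ALT, AST, total bilirubin and suspected Hy's Law = 4. TSH or FT4: 0.
- Laboratory listing: markedly abnormal values only, so it inherits the 0 from Attachment 4.

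**Step 3. How general the gap is**

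Insulin is in the protocol's chemistry panel and also has no Attachment 4 row, although SAP 6.2.1 uses it for HOMA. Analytes that do have limits are affected too. The creatinine limit is 3 mg/dL. If the laboratory's upper limit is below that, a creatinine between the two would be listed under the protocol but not under the SAP.

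**Step 4. Indirect routes for TSH**

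- Adverse events: these are tabulated by preferred term and by lowest level term, but an abnormal TSH enters only if the investigator judges the change clinically relevant.
- Minimum and maximum: SAP 4.1 and 6.3 include them in descriptive statistics. SAP 6.2 does not say so. If they are shown, they reveal an extreme value but neither count nor identify subjects.
- Number with FT4: it mixes treated hypothyroidism with elevated TSH, misses low TSH and identifies nobody. For the same reason, FT4 arm means describe a selected subset.

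Only the adverse event route produces a count or a name, and it depends on judgement.

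**The case against.** The strongest reply is that the protocol's listing has not been withdrawn. Protocol 11.8 is current text, and a listing of any out-of-range result would include TSH. A reader might infer that no planned output anywhere could name a subject with abnormal TSH. The documents do not support that. The accurate statement is that the SAP, which describes itself as complete for the report, does not carry the listing over. Table shells outside these documents might still include it.

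A reader might also take this as a thyroid-specific failing. It is not: the omission covers all analytes, and TSH is neither a listed metabolic endpoint nor an adverse event of special interest. Uncontrolled thyroid disease is excluded at entry.

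Nor can a thyroid signal be inferred. Amendment 1 added two references alongside its toxicology results, one on endocrine toxicity and one on altered thyroid function in rats. The toxicology text is redacted, and a reference title shows a topic, not a finding.

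Finally, protocol 11.8 does not prescribe a shift table, so that part of the remedy is an improvement rather than a restored commitment. Investigator review also gives real partial coverage. All of this limits the weight of the point. None of it puts the missing listing or reference-range summary into the SAP.

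**Conclusion.** The point holds as a minor mismatch between protocol and SAP. One of two promised laboratory listings and the general use of reference ranges are missing from SAP 6.2. TSH and FT4 are covered by none of the 38 limits, 13 shifts or 4 ULN-based counts. Under the SAP alone, new abnormal TSH would be counted only through investigator-reported adverse events.

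This rests on two things: that the SAP governs what is produced, as its introduction says, and that the protocol text still stands, since no recorded change withdraws it. The primary endpoint and its analysis are unaffected. A reader might expect the added table to test for a difference between arms. It would be descriptive only, and it would not remove any imbalance in numbers tested that discontinuation causes.

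**What to change.** In SAP 6.2:

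1. Restore the protocol's listing of subjects with any laboratory result outside the reference ranges, for all analytes, showing FT4 beside TSH.
2. Add a descriptive TSH shift table (low, normal, high) against the central laboratory range, from baseline to Week 12, Week 24 and End point (DB). Give treatment-emergent high and low counts by arm over the number tested. SAP Table 1 already defines these windows for TSH.
3. Footnote the FT4 summaries as a selected subset: treated hypothyroidism or elevated TSH.

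The cost is one listing, one table and one footnote. TSH and FT4 are already measured by the central laboratory, so no new data are needed. Item 1 closes the clearest mismatch. Items 2 and 3 make the thyroid data interpretable.

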1.1. Trial Objectives

Objectives	Endpoints
Primary	

 To assess, in subjects with major depressive disorder (MDD) who have had an inadequate response to current antidepressant therapy with a selective serotonin reuptake inhibitor (SSRI) or serotonin-norepinephrine reuptake inhibitor (SNRI), the efficacy of flexibly dosed JNJ-42847922 (20 mg or 40 mg) compared to flexibly dosed quetiapine extended-release (XR) (150 mg or 300 mg) as adjunctive therapy to an antidepressant drug in delaying time to all-cause discontinuation of study drug over a 6-month (24-week) treatment period. 	
 Time to all-cause discontinuation of study drug.
Secondary	

 To assess the efficacy of JNJ-42847922 compared to quetiapine XR in the adjunctive treatment of MDD based on: 
 Achieving and sustaining remission of depressive symptoms Achieving and sustaining response of depressive symptoms Improving depressive symptoms in subjects with significant insomnia versus those without significant insomnia 	
 The proportion of subjects achieving (at Week 12) and sustaining remission at Weeks 18 and 24. Remission is defined as Montgomery-Asberg Depression Rating Scale (MADRS) total score ≤ 12. The proportion of subjects achieving (at Week 12) and sustaining response at Weeks 18 and 24. Response is defined as $\geq 50\%$ improvement from baseline MADRS total score. Change from baseline to Weeks 12, 18, and 24 in the MADRS total score in subjects with significant insomnia (baseline Insomnia Severity Index [ISI] score ≥ 15) versus those without significant insomnia (baseline ISI

Objectives	Endpoints
	score <15).

 - Improving anxiety symptoms 	
 - Change from baseline to Weeks 12, 18, and 24 in the 14-item Hamilton Anxiety Rating Scale (HAM-A) total score.

 • To assess the effect of JNJ-42847922 compared to quetiapine XR as adjunctive therapy for MDD on metabolic parameters during long-term (6 months) treatment, including: 	

 - Weight 	
 • The proportion of subjects with weight gain $\geq 7\%$ of baseline body weight at end-of-study assessment.

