
 - Lipids 	
Triglycerides
 
 • The proportion of subjects with shifts in triglycerides from normal to high (<150 mg/dL at baseline to ≥ 200 mg/dL at any post-baseline assessment). • The proportion of subjects with shifts in triglycerides from borderline to high (≥ 150 and <200 mg/dL at baseline to ≥ 200 mg/dL at any post-baseline assessment). • The proportion of subjects with shifts in triglycerides from normal to very high (<150 mg/dL at baseline to ≥ 500 mg/dL at any post-baseline assessment). • The proportion of subjects with shifts in triglycerides from borderline to very high (≥ 150 mg/dL and <200 mg/dL at baseline to ≥ 500 mg/dL at any post-baseline assessment). • The proportion of subjects with shifts in triglycerides from high to very high (≥ 200 mg/dL and <500 mg/dL at baseline to ≥ 500 mg/dL at any post-baseline assessment).

 - Blood Glucose 	
Fasting glucose
 
 • The proportion of subjects with shifts in fasting blood glucose from normal to borderline (<100 mg/dL at baseline to ≥ 100 and <126 mg/dL at any post-baseline assessment). • The proportion of subjects with shifts in fasting blood glucose from borderline to high (≥ 100 to <126 mg/dL at baseline to

Objectives	Endpoints
	
≥126 mg/dL at any post-baseline assessment).
 
 The proportion of subjects with shifts in fasting blood glucose from normal to high (<100 mg/dL at baseline to ≥126 mg/dL at any post-baseline assessment).

 To assess the efficacy of JNJ-42847922 compared to quetiapine XR as adjunctive therapy for MDD in the improvement of global depressive symptom severity. 	
 Change from baseline to Weeks 12 and 24 in the Clinical Global Impression-Severity (CGI-S) score.

 To characterize subject perceptions of global MDD severity. 	
 Change from baseline to Weeks 12 and 24 in the Patient Global Impression-Severity (PGI-S) score.

 To assess the effect of JNJ-42847922 compared to quetiapine XR as adjunctive therapy for MDD on the subject's assessment of quality of life. 	
 Change from baseline to Weeks 12 and 24 in Quality of Life in Depression Scale (QLDS).

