1.4. Sample Size Justification

The primary purpose of the study is to investigate potential differentiating features between JNJ-42847922 and quetiapine XR. Although the sample size was not chosen based on a specific

set of endpoints, for evaluating the time to discontinuation of study drug in the JNJ-42847922 group versus the quetiapine XR group, a one-sided log-rank test with an overall sample size of 100 subjects (50 in the JNJ-42847922 group and 50 in the quetiapine XR group) provides approximately 92% power at a 1-sided 0.10 significance level to detect a hazard ratio of 0.415, assuming the proportion of subjects who discontinue from study drug in the quetiapine XR group is 50%. The planned sample size of the study is consistent with the nature of a Phase 2 exploratory study.

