6.3. Vital Signs and Physical Examination Findings

Continuous vital sign variables including weight, waist circumference, temperature, supine and standing pulse, supine and standing blood pressure (systolic and diastolic), and BMI will be summarized at each assessment time point by treatment group. BMI will be calculated as weight (kg)/(height (m))², at each time point that body weight is measured. The height measurement collected at screening will be used in the calculation. Changes from baseline to each postbaseline time point will be summarized. Descriptive statistics (N, mean, SD, median, minimum and maximum) will be presented.

Incidence of treatment-emergent clinically important abnormalities in vital signs during the double-blind phase, as defined in Table 6, will be summarized for subjects who had at least one postbaseline assessment for that vital sign. If the baseline value is missing, the postbaseline value will be compared against the abnormally low/abnormally high criteria. Vital sign assessments collected during follow-up will not be used for this summary.

Table 6: Clinically Important Abnormalities in Vital Signs

Vital Sign Parameter	Postbaseline value outside of normal limit if:
----------------------	--

	Abnormally low	Abnormally high
Pulse (bpm)	A decrease from baseline of ≥ 15 to a value ≤ 50	An increase from baseline of ≥ 15 to a value ≥ 100
Systolic BP (mmHg)	A decrease from baseline of ≥ 20 to a value ≤ 90	An increase from baseline of ≥ 20 to a value ≥ 180
Diastolic BP (mmHg)	A decrease from baseline of ≥ 15 to a value ≤ 50	An increase from baseline of ≥ 15 to a value ≥ 105
Body weight (kg)	A decrease from baseline of $\geq 7\%$	An increase from baseline of $\geq 7\%$
Body temperature ($^{\circ}\text{C}$)	$< 35.5^{\circ}\text{C}$	$> 37.5^{\circ}\text{C}$

BP = blood pressure

A listing of subjects with treatment-emergent clinically important abnormalities in vital signs will be presented.

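### The secondary objective comparing the two drugs on weight, triglycerides and fasting glucose has no pre-specified between-drug estimate or interval, and the laboratory shifts have no stated at-risk denominator

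*SAP*

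**What the plan says.** The secondary objective in SAP 1.1, which matches Protocol 2.1, reads "To assess the effect of JNJ-42847922 compared to quetiapine XR as adjunctive therapy for MDD on metabolic parameters during long-term (6 months) treatment". It has nine endpoints, all proportions:

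- **Weight (one):** gain of at least 7% "of baseline body weight at end-of-study assessment".
- **Triglycerides (five):** beginning with "The proportion of subjects with shifts in triglycerides from normal to high".
- **Fasting glucose (three):** beginning with "The proportion of subjects with shifts in fasting blood glucose from normal to borderline".

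General safety and tolerability is a separate secondary objective with its own endpoint list.

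The metabolic endpoints are analysed only in the SAP's safety chapter. For the shifts, section 6.2 states that "the number of subjects with the following shifts in chemistry laboratory values from baseline to the maximum postbaseline time point will be presented". That sentence does not itself mention treatment group; display by arm is inferred from the rest of 6.2 and from Protocol 11.8. Other chemistry and lipid results get descriptive statistics. For weight, section 6.3 says "Changes from baseline to each postbaseline time point will be summarized", with N, mean, SD, median and range. Its Table 6 adds the incidence of a gain of 7% or more during the double-blind phase, among subjects with at least one postbaseline weight.

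SAP 5.1.1 promises point estimates and confidence intervals, but only for efficacy endpoints. Table 4, the list of efficacy variables, does not contain the metabolic ones.

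**The concern.** The question asked is a contrast between drugs, and the planned output is one summary per drug. SAP 1.4 states that "The primary purpose of the study is to investigate potential differentiating features between JNJ-42847922 and quetiapine XR", so the size of a metabolic difference, and how well it is known, belongs to what the study is meant to deliver. If the contrast is not pre-specified, whoever writes the report chooses the effect measure, the denominator, the visit and the adjustment after unblinding.

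Two narrower gaps sit beside it. A shift is defined from a starting category, so its natural denominator is the subjects who began there; section 6.2 names none and promises a number where the endpoint is a proportion. The weight endpoint is tied to one assessment, but Table 6 counts a gain at any time in the phase, so the endpoint as defined may not be produced.

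**Working it through.** **1. Is the contrast planned anywhere?**

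- SAP 1 says the plan covers all analyses for the study report except biomarker, pharmacogenomic, and pharmacokinetic or exposure-response work. Nothing defers the metabolic comparison elsewhere.
- SAP 5.3.2.2 and 5.3.3.2 give sustained remission and sustained response, which are also secondary proportions, a Mantel-Haenszel estimate with an 80% CI controlling for insomnia status.
- SAP 5.3.1.2 gives MADRS change an LS-mean difference with an 80% CI from a repeated-measures model, and most other continuous secondary scales reuse it.
- SAP 6.2 limits its liver-test incidences to subjects below the threshold (or missing) at baseline. The at-risk device is therefore in the same section but is not applied to the shifts.

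**2. The plan's own figure.** The only power statement (SAP 1.4) is for time to discontinuation: 50 per arm, 50% discontinuing on quetiapine XR, hazard ratio 0.415, one-sided 0.10.

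- Discontinuing on JNJ-42847922: 1 - 0.50^0.415 = 0.25.
- Events: 50 × 0.50 + 50 × 0.25 = 37.5.
- Schoenfeld: √37.5 × |ln 0.415| / 2 - 1.2816 = 2.693 - 1.282 = 1.411, so power is 0.921. The stated 92% reproduces.

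No such figure exists for the metabolic endpoints. The same assumptions imply about 25 completers on quetiapine XR and about 37 on JNJ-42847922.

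**3. The interval that could be reported.** The documents give no metabolic event rates, so the rates here are assumptions. The 80% Wald interval for a risk difference is d ± 1.2816 × √[p1(1-p1)/n + p2(1-p2)/n]. For 5% versus 15% with n = 50: √(0.00095 + 0.00255) = 0.0592, half-width 0.076.

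| Assumed rates | Difference (points) | 80% CI, 50 per arm | 80% CI, 25 per arm |
|---|---|---|---|
| 5% vs 5% | 0 | -5.6 to 5.6 | -7.9 to 7.9 |
| 5% vs 15% | 10 | 2.4 to 17.6 | -0.7 to 20.7 |
| 5% vs 20% | 15 | 6.7 to 23.3 | 3.3 to 26.7 |
| 10% vs 30% | 20 | 10.1 to 29.9 | 6.0 to 34.0 |

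The 25-per-arm column stands for fewer subjects at risk or fewer remaining at the end.

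**4. What the denominator does.** Assume 60% of 50 per arm start in the normal category.

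- *Dilution.* With 30 at risk per arm and true rates of 5% and 15%, expected counts are 1.5 and 4.5. Over 50 these read 3% and 9%, a 6-point difference instead of 10.
- *Chance imbalance.* The between-arm difference in numbers at risk has SD √(2 × 50 × 0.6 × 0.4) = 4.9. A difference of 6 or more has probability about 2 × [1 - Φ(5.5/4.9)] = 0.26. With 33 versus 27 at risk and the same 15% rate in both arms, expected counts are 4.95 and 4.05: 9.9% and 8.1% of 50, a spurious 1.8 points.

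Dilution is the larger effect; imbalance is small against the intervals in step 3.

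**5. Sparse shifts.** Protocol 4.2 excludes fasting triglycerides of 500 mg/dL or more at screening, so shifts to that level may be few. If 10 per arm were at risk with a 2% to 5% rate (assumed), neither arm would have an event with probability 0.95^20 = 0.36 to 0.98^20 = 0.67. A Wald interval would then have zero width.

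**The case against.** The strongest reply is that descriptive safety reporting is customary, that the study is labelled a Phase 2 exploratory one, and that Protocol 11.8 already says weight changes will be summarised descriptively. The general safety objective is also worded as a comparison and is handled descriptively throughout, so comparative wording alone does not promise inference here. This stands as a reason not to call the plan wrong. It does not remove the case for estimation: the metabolic endpoints were given their own objective and exact definitions, and 80% intervals without multiplicity control are already this SAP's convention.

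Three stronger readings are tempting, and the documents do not support them.

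- *The report could not show how large the difference is.* N, mean and SD for each arm are planned for weight and the laboratory values, and a reader can form a crude difference and 80% CI from them. A stratified or baseline-adjusted difference cannot be recovered from the planned tables, nor can an at-risk risk difference unless the denominators are printed.
- *Weight gain lacks a denominator.* Table 6 supplies one, and no starting category applies to weight. What is missing is the contrast and the match to the endpoint's timing.
- *Metabolic effects are the main expected difference.* Protocol 1.4 and 3.2 list them beside akathisia and extrapyramidal symptoms, and 1.4 adds sexual side effects. No ranking is given.

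Nor is the power lost by cutting weight change at 7% a measure of this gap. That is a question about dichotomising, and it needs means and SDs that the documents do not give.

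**Conclusion.** The point holds as a gap in pre-specified estimation. For a named comparative secondary objective, the SAP plans no between-drug estimate or interval for weight, triglycerides or fasting glucose. It leaves the shift denominators unstated, and it summarises the 7% weight endpoint over a different period from its definition. This follows from the text and needs no assumption.

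The size can only be illustrated. With 50 per arm and assumed rates of 5-10% against 5-30%, the omitted 80% intervals have half-widths of about 6 to 10 points; with 25 per arm, about 8 to 14. An all-subjects denominator could shrink a 10-point shift difference to 6 if 60% start in the category. The primary analysis and its error rate are untouched. The change is worth making because it is cheap and lets the trial answer its own question with stated precision.

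**What to change.** 1. In SAP 6.2, report each glucose and triglyceride shift by treatment group as a number and a percentage of subjects who were in the stated baseline category and have a postbaseline value.
2. For weight gain of 7% or more at the end-of-study assessment, and for the more common shifts, give the between-arm risk difference with an 80% CI, stratified by insomnia status where counts allow. State which analysis visit serves as that assessment: SAP Table 1 has no follow-up window for weight. For sparse shifts, such as those to 500 mg/dL or more, use an unstratified exact or score interval, or counts only, and state the rule for choosing in advance.
3. Apply the SAP 5.3.1.2 repeated-measures model to change in weight, log triglycerides and fasting glucose, each with its own baseline as covariate, and report the LS-mean difference with an 80% CI at Weeks 12 and 24.

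The data are already scheduled at baseline and Weeks 6, 12 and 24, and the methods are already in the SAP. The cost is wording, modest programming and more nominal intervals without multiplicity adjustment, which the SAP should label as such.
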